## Appendix 1. Summary of Efficacy Analyses

Endpoint	Analysis Type	Population	Data Inclusion and Rules for Handling Intercurrent Events and Missing Data	Analysis Model
Proportion of participants with RSV-related hospitalization or death from any cause through Day 28	Summary statistics	mITT-infected	All data collected will be included regardless of intercurrent events.	NA
Proportion of participants with RSV-related visits (urgent care/ED/hospital) or death from any cause through Day 28	Summary statistics	mITT-infected	All data collected will be included regardless of intercurrent events.	NA
Proportion of participants with progression of LRTI through Day 10	Summary statistics	mITT-infected with no LRTI or only nsLRTI at randomization	All data collected will be included regardless of intercurrent events.	NA
Proportion of participants with development of LRTI through Day 10	Summary statistics	mITT-infected with no LRTI at randomization	All data collected will be included regardless of intercurrent events.	NA
Proportion of participants with resolution of LRTI at Day 15	Summary statistics	mITT-infected with nsLRTI or sLRTI at randomization	All data collected will be included regardless of intercurrent events.	NA
Mean number of hospital- free days through Day 28	Summary statistics	mITT-infected	All data collected will be included regardless of intercurrent events.	NA

[figure not shown]
Proportion of participants with progression of LRTI through each visit	Summary statistics	mITT-infected with no LRTI or only nsLRTI at randomization	All data collected will be included regardless of intercurrent events.	NA
Proportion of participants with development of LRTI through each visit	Summary statistics	mITT-infected with no LRTI at randomization	All data collected will be included regardless of intercurrent events.	NA
Proportion of participants with resolution of LRTI at each visit	Summary statistics	mITT-infected with nsLRTI or sLRTI at randomization	All data collected will be included regardless of intercurrent events.	NA
Proportion of participants with improvement in LRTI status at each visit	Summary statistics	mITT-infected with nsLRTI or sLRTI at randomization	All data collected will be included regardless of intercurrent events.	NA
Summary of RSV related days in hospital through Day 28	Summary statistics	mITT-infected	All data collected will be included regardless of intercurrent events. No imputation will be performed for missing data.	NA
Summary of RSV related days in ICU through Day 28	Summary statistics	mITT-infected	All data collected will be included regardless of intercurrent events. No imputation will be performed for missing data.	NA
Proportion of participants with a clinical response of Improvement or Resolution by visit	Summary statistics	mITT-infected	All data collected will be included regardless of intercurrent events.	NA

Proportion of participants with undetectable RSV viral load by visit	Summary statistics	mITT-infected	All data collected will be included regardless of intercurrent events. No imputation will be performed for missing data.	NA
Change from baseline in RSV viral load by visit	Summary statistics	mITT-infected	All data collected will be included regardless of intercurrent events. No imputation will be performed for missing data.	NA

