#### 3.2. Secondary Endpoints

## 3.2.1. Efficacy Endpoints

#### 3.2.1.1. Key Secondary Endpoints

All key secondary endpoints are evaluated in the mITT-infected analysis set.

 Proportion of participants with RSV-related visits (urgent care/ED/hospital) or death from any cause through Day 28

For this secondary endpoint, no minimum duration of hospitalization is required. If a patient is located in an urgent care or ED at time of randomization, that initial visit would not count towards assessment of this endpoint.

Proportion of participants with progression of LRTI through Day 10

Presence of LRTI is assessed at each clinic visit. If present, the investigator also records on the CRF if it is nsLRTI or sLRTI. This designation is used in LRTI analyses and is not the assessment of intensity grading of the LRTI.

Progression of LRTI is defined as progressing from no LRTI at randomization to nsLRTI or sLRTI, or from nsLRTI at randomization to sLRTI, at any time up to and including Day 10.

Proportion of participants with development of LRTI through Day 10

Development of LRTI is defined as not having LRTI at randomization but having nsLRTI or sLRTI at any time up to and including Day 10.

Proportion of participants with resolution of LRTI at Day 15

Resolution of LRTI is defined as having nsLRTI or sLRTI at randomization and having no LRTI at Day 15.

Mean number of days alive and free from hospital stay (hospital-free days) through Day
 28

All hospital days will be counted, regardless of whether or not the hospital admission or hospital day is related to RSV.

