## 3.2.1.2. Other Efficacy-Related Secondary Endpoints

Secondary endpoints in this section are evaluated in the mITT-infected analysis set.

- Proportion of participants with progression of LRTI through Day 3, 5, 15, and 28
- Proportion of participants with development of LRTI through Day 3, 5, 15, and 28
- Proportion of participants with resolution of LRTI at Day 3, 5, 10, and 28
- Proportion of participants with improvement in LRTI status at Day 3, 5, 10, 15, and 28

Improvement in LRTI status is defined as having nsLRTI at randomization and having no LRTI at the Day of interest, or having sLRTI at randomization and having nsLRTI or no LRTI at the Day of interest.

- Number of RSV related days in hospital through Day 28.
- Number of RSV related days in ICU through Day 28.
- Proportion of participants with a clinical response of Improvement or Resolution at Day 5, 10, 15, and 28.
- Proportion of participants with undetectable RSV viral load at each study visit through Day 28.

Undetectable RSV viral load at a visit is defined as a central PCR laboratory result of 'TND' (or, a converted numeric value of 0, see below) for both subtype A and subtype B at that visit.

Change from baseline in RSV viral load at each study visit through Day 28.

For numeric viral load summaries, numeric values in units of copies/mL will first be derived from the possible categorical results as follows:

0	If the result is 'TND' (target not detected <lod), a="" applicable="" as="" be="" cci="" cci<="" of="" th="" used,="" value="" will=""></lod),>
0	If the result is 'TD' (target detected <lloq), cci<="" th=""></lloq),>
0	If the result is CCI
	Such values may ultimately be replaced by
	numeric results in subsequent data transfers.

Then for each participant and visit, the total unlogged numeric viral load value will be the sum of the unlogged values, ie, those expressed in units of copies/mL, from subtype A and subtype B. For use in summaries, this total unlogged numeric viral load value will then be transformed to log10 copies/mL, and change from baseline will be calculated from the log10 values. If the sum of the unlogged values is 0, then the transformed value will be set to 0 log10 copies/mL.

See Appendix 2.1 for definition of baseline.

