#### 6.2.1.1.2.1. Main Analysis

- Estimand strategy: treatment policy and composite (section 2.2.2.1).
- Analysis set: mITT-infected (section 4). Participants must have either no LRTI or only nsLRTI at randomization.
- Analysis methodology: Proportion of participants will be summarized (section 5.2).
- Intercurrent events and missing data: The intercurrent events "discontinuation from or non-compliance to the planned course of treatment," "discontinuation from the study," and "initiation of rescue or other concomitant medications" are addressed by including all available data in the analysis regardless of discontinuation, non-compliance, or use of concomitant medications. The composite strategy is followed for the intercurrent event of "death" by incorporating death into the endpoint, ie, death will be considered progression of LRTI. The intercurrent event of "RSV-related hospitalization" after first dose of study medication will also be considered progression of LRTI.
- Results will be presented similarly to those for the primary endpoint (section 6.1.1.1).

#### 6.2.1.1.3. Development of LRTI through Day 10

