#### 6.2.1.1.4.1. Main Analysis

- Estimand strategy: treatment policy and composite (section 2.2.2.1).
- Analysis set: mITT-infected (section 4). Participants must have either nsLRTI or sLRTI at randomization.
- Analysis methodology: Proportion of participants will be summarized (section 5.2).
- Intercurrent events and missing data: The intercurrent events "discontinuation from or non-compliance to the planned course of treatment," "discontinuation from the study," and "initiation of rescue or other concomitant medications" are addressed by including all available data in the analysis regardless of discontinuation, non-compliance, or use of concomitant medications. The composite strategy is followed for the intercurrent event of "death" by incorporating death into the endpoint, ie, death will be considered "not resolved". The intercurrent event of "RSV-related hospitalization" after first dose of study medication will also be considered as LRTI "not resolved".
- Results will be presented similarly to those for the primary endpoint (section 6.1.1.1).

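### Does SAP Appendix 1 give the LRTI endpoints a second scoring rule by leaving out the death and hospitalization composite?

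*SAP*

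**What the plan says.** **SAP 2.2.2 and 6.2.1.1.** The progression, development and resolution estimands each treat death as failure and then add a hospitalization rule. For progression, RSV-related hospitalization "after first dose of study medication will also be considered progression of LRTI". For resolution, it "after first dose of study medication will also be considered as LRTI" not resolved. Development is worded in parallel. SAP 2.2.2.2 does the same for improvement, and SAP 6.2.1.2 sends improvement and clinical response to the resolution methods.

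**SAP 3.2.1.** The definitions use LRTI status as recorded at clinic visits (nsLRTI or sLRTI) and mention no composite. For example: "Resolution of LRTI is defined as having nsLRTI or sLRTI at randomization and having no LRTI at Day 15". The improvement definition in 3.2.1.2 is built the same way: "Improvement in LRTI status is defined as having nsLRTI at randomization and having no LRTI at the Day of interest".

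**SAP Appendix 1.** Under the heading "Data Inclusion and Rules for Handling Intercurrent Events and Missing Data", every efficacy row carries the sentence "All data collected will be included regardless of intercurrent events". Four rows (RSV-related hospital days, ICU days and the two viral-load endpoints) add that nothing is imputed.

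**Protocol 9.1.1.2 and SAP 2.1.** The protocol estimands for progression, development and resolution count death as failure but do not mention hospitalization. SAP 2.1 discloses the move to all-cause LRTI and does not mention the hospitalization component.

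**The concern.** The Appendix 1 column claims to give the handling rules. The SAP itself names both death and RSV-related hospitalization as intercurrent events for these endpoints. Taken word for word, the sentence disregards the very events that the body of the SAP scores as failures, and the section 3 definitions do not restore them.

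Three of the five key secondary endpoints are involved. With no testing planned, the proportions by arm are the efficacy result. On the literal reading, a participant with LRTI at randomization who is admitted on Day 2 and is free of LRTI at Day 15 would count as resolved. A participant admitted for RSV-related cardiac decompensation, with no LRTI recorded at any visit, would count as neither progression nor development. A participant who died would have no Day 15 status, and SAP 5.3 has no missing-data rule for efficacy. The most serious outcomes could then leave the failure counts, contrary to the protocol's own treatment of death.

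**Working it through.** No figure in the plan can be reproduced here. The check compares texts and then sizes the literal reading.

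**Step 1: how far the sentence reaches.** Appendix 1 has 15 rows and the sentence is in all of them.

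| Rows | Composite in the detailed sections | Composite visible in the row name |
|---|---|---|
| Primary; RSV-related visits (2) | Death | Yes |
| Progression, development, resolution, key secondary (3) | Death and RSV-related hospitalization | No |
| Progression, development, resolution, improvement by visit (4) | Death and RSV-related hospitalization | No |
| Hospital-free days (1) | Death | No; the row name omits the word alive |
| Clinical response (1) | Only through the cross-reference to resolution methods | No |
| Hospital days, ICU days, two viral-load endpoints (4) | None stated | Not applicable |

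2 + 3 + 4 + 1 + 1 + 4 = 15. The LRTI rows number 3 + 4 = 7.

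**Step 2: test the literal reading on row 1.** SAP 2.2.1 classes death as an intercurrent event, and the primary endpoint's name includes death. If the sentence meant that intercurrent events are not scored, row 1 would contradict its own endpoint. The hospital-free-days row would likewise lose the death composite given in SAP 2.2.2.1 and 6.2.1.1.5.1. The sentence can therefore only mean that data are kept after such events. It does not say how death or admission is scored.

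**Step 3: compare with the long form.** In SAP 6.2.1.1.2.1, 6.2.1.1.3.1 and 6.2.1.1.4.1, a single bullet first includes all available data whatever the discontinuation, non-compliance or concomitant medication, and then states the composite. The first part governs which data enter and the second builds the endpoint. Appendix 1 shortens the first part.

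**Step 4: look for a deliberate change.** The version history lists Appendix 1 among the sections edited to remove inferential analyses and imputation and to simplify rescue-medication handling. It records no removal of the composite.

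**Step 5: size of the literal reading, if someone used it.** There are 4 LRTI endpoints at 5 days each (3, 5, 10, 15, 28), so 4 × 5 = 20 rates per arm. Clinical response would add 4 more only if it inherits the composite. Three illustrations follow. In the second and third, an event is assumed to count only from the endpoint day on or after it, a limit the SAP does not state:

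- sLRTI at randomization and still present at Days 3 and 5, admitted Day 2, no LRTI from Day 10: resolution and improvement differ at Days 10, 15 and 28, so 2 × 3 = 6 entries (9 if clinical response is included and rated favourably on those days).
- No LRTI at any visit, RSV-related cardiac admission on Day 4: progression and development differ at Days 5, 10, 15 and 28, so 2 × 4 = 8 entries.
- No LRTI recorded, death on Day 8: progression and development differ at Days 10, 15 and 28, so 2 × 3 = 6 entries.

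One participant moves a rate by 100/n points: n = 5 gives 20, n = 10 gives 10, n = 20 gives 5. These n are assumptions; the SAP says only that very few participants were enrolled. It does not say whether any admission or death occurred.

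**Step 6: result when the detailed sections are followed.** Every LRTI illustration is scored as failure under SAP 2.2.2 and 6.2.1.1. Editing Appendix 1 would leave all of those entries the same.

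**The case for a change.** The best case for a change is that the column heading promises the rules for intercurrent events, that the LRTI row names (unlike those of the first two rows) give no hint of a composite, and that no sentence says which section governs. The derivations are deferred to an Analysis and Reporting plan that is not among these documents. Protocol Table 4 makes need for hospitalization a criterion for severe LRTI, but only where LRTI is present, so it narrows the gap without closing it.

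What stands is that the table is incomplete and the section 3 definitions carry no cross-reference. It does not stand that the endpoints can properly be produced two ways. To get the second answer, an analyst would have to set a one-line summary above the estimand section and the analysis section, which agree endpoint by endpoint and match the protocol on death.

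The omission from SAP 2.1 is real. It is somewhat awkward because 2.1 argues against relying on the investigator's view of RSV-relatedness, while under protocol 8.2.1 the hospitalization component depends on that view. But the primary endpoint rests on the same judgement, protocol section 9 lets the SAP modify the outlined analyses, and an amendment is required only for major changes to the primary endpoint or its analysis. The added component is stated openly in SAP 2.2.2 and again in 6.2.1.1.

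Two smaller points remain open whatever Appendix 1 says: whether clinical response inherits a composite worded for LRTI, and whether an admission after the endpoint day counts. The SAP says only that it follows the first dose. These are derivation details that analysts ordinarily settle in programming specifications.

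**Conclusion.** No change to the plan follows. The summary table is terse and the list of modifications in SAP 2.1 is one item short, but the operative sections give a single scoring rule for each LRTI endpoint. Cross-references would be tidier and would alter no reported proportion. The 20-to-5-point shift per participant arises only if the table is read against the rest of the SAP, with an assumed 5 to 20 participants in the LRTI subset of an arm. The study was discontinued early, no inferential testing is planned, and no decision rests on these summaries. The conclusion assumes that the Analysis and Reporting plan, not available here, follows SAP 2.2.2 and 6.2.1.1.

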#### Appendix 2. Data Derivation Details

## Appendix 2.1. Definition and Use of Visit Windows in Reporting

The following table defines the visit windows and labels to be used for reporting other than endpoints assessed for an event through Day 28 (those endpoints use a window of Day 1 to Day 28) and PK endpoints (those endpoints use nominal visit):

- Labs, Viral load, Vital Signs, and LRTI: Baseline window will be Day -2 to 1 without any consideration to the time factor. The only
  exception to time is viral load, where baseline is within 1 hour post start of dosing. If both screening and Day 1 visits are
  collected on the same calendar day, Day 1 will be used.
- If multiple readings fall into the same window on different days, choose the one closer to the target day. If equidistant, then select
  the later one after the target day. If multiple readings fall into the same window on the same day at study start, pick Day 1 as the
  nominal visit over screening for baseline. For vital signs, average the readings if they are on the same day within 10 minutes.
- For labs and viral load, if multiple observations without time or at the same time fall on the same day after the windowing logic has been applied, average observations. If different times on the same day, select the later one.
- When data from study Day 4 has an overlap between Day 3 and Day 5 windows, decision made is to assign the window
  according to the nominal visit. The rule will not be applicable to other study days 2 and 3 for Day 3 window, and days 5 and 6 for
  Day 5 window.
- If unplanned viral load (or other outcomes) are assessed on Day 4, then it will be assigned to Day 3. If the nominal Day 3 exists
  and an unplanned Day 4 assessment is obtained, then the nominal Day 3 visit will still be chosen as the record for the Day 3
  window.

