8.2.4. RSV-related lower respiratory tract infection

Signs and symptoms of RSV will be collected by the Investigator per the [SoA](#) (Section 1.3) during scheduled visits. Criteria for diagnosis of LRTI are provided in Table 3. Criteria for diagnosis of severe LRTI (sLRTI) are provided in [Table 4](#) [14]. Intensity grading displayed in [Table 5](#) is a component of the severe LRTI criteria. An episode of LRTI that does not meet criteria for sLRTI is considered non-severe LRTI (nsLRTI). Investigators will determine if sLRTI or nsLRTI is related to RSV (referred to as sLRTI-RSV and nsLRTI-RSV).

- Development of LRTI is defined as transitioning from not having LRTI at randomization to having nsLRTI-RSV or sLRTI-RSV.
- Progression of LRTI is defined as development of LRTI or transitioning from nsLRTI-RSV at randomization to sLRTI-RSV.
- Resolution of LRTI is defined as transition from nsLRTI-RSV or sLRTI-RSV at randomization to not having nsLRTI-RSV and not having sLRTI-RSV.
- Improvement in LRTI status is defined as LRTI resolution or transition from sLRTI-RSV at randomization to nsLRTI-RSV.

Table 3. Criteria for LRTI

LRTI is defined as:	

• ≥ 2 lower respiratory signs or symptoms for at least 24 hours including at least 1 lower respiratory sign;	
Or	

• 3 lower respiratory symptoms for at least 24 hours.	
Lower respiratory symptoms	Lower respiratory signs

• New or increased sputum.• New or increased cough.• New or increased dyspnea (shortness of breath).	
• New or increased wheezing.• New or increased crackles/ronchi based on chest auscultation.• Respiratory rate ≥ 20 respirations/minute.• Low or decreased oxygen saturation ($O_2 < 95\%$ or $\leq 90\%$ if pre-season baseline is $< 95\%$).• Need for new or increased oxygen supplementation.

Table 3. Criteria for LRTI

LRTI is defined as:

• ≥ 2 lower respiratory signs or symptoms for at least 24 hours including at least 1 lower respiratory sign;
Or

• 3 lower respiratory symptoms for at least 24 hours.

Criteria for LRTI are based on Papi, et al. 2023 [14].

Table 4. Criteria for severe LRTI

Severe LRTI is defined as the presence of LRTI with at least one of the following criteria:

• ≥ 2 lower respiratory signs.

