#### 6.2.1.2. Other Efficacy-Related Secondary Endpoints

Proportion of participants with progression of LRTI through Day 3, 5, 15, and 28

These endpoints will be summarized with the same methods as the similar endpoint through Day 10 (section 6.2.1.1.2.1).

Proportion of participants with development of LRTI through Day 3, 5, 15, and 28

These endpoints will be summarized with the same methods as the similar endpoint through Day 10 (section 6.2.1.1.3.1).

Proportion of participants with resolution of LRTI at Day 3, 5, 10, and 28

These endpoints will be summarized with the same methods as the similar endpoint at Day 15 (section 6.2.1.1.4.1).

Proportion of participants with improvement in LRTI status at Day 3, 5, 10, 15, and 28

These endpoints will be summarized with the same methods as the endpoint of resolution of LRTI at Day 15 (section 6.2.1.1.4.1).

Number of RSV related days in hospital through Day 28.

Health resource utilization data will be summarized by treatment group. This will include number of days of RSV related hospital stay through Day 28. The analyses will be done using the mITT-infected population. Descriptive statistics (ie, mean, SD, median, range) will be used to summarize this endpoint. No imputation for missing data will be performed for participants who discontinue or die prior to the Day 28 visit; the count of RSV related hospital days will be truncated at the date of discontinuation or death.

Number of RSV related days in ICU through Day 28.

Health resource utilization data will be summarized by treatment group. This will include number of days of RSV related ICU stay through Day 28. The analyses will be done using the mITT-infected population. Descriptive statistics (ie, mean, SD, median, range) will be used to summarize this endpoint. No imputation for missing data will be performed for participants who discontinue or die prior to the Day 28 visit; the count of RSV related ICU days will be truncated at the date of discontinuation or death.

 Proportion of participants with a clinical response of Improvement or Resolution at Day 5, 10, 15, and 28.

These endpoints will be summarized with the same methods as the endpoint of resolution of LRTI at Day 15 (section 6.2.1.1.4.1). The analysis set is the mITT-infected analysis set (section 4).

 Proportion of participants with undetectable RSV viral load at each study visit through Day 28.

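### Read literally, the SAP's Day 1 to Day 28 window leaves out LRTI first recorded at a protocol-compliant Day 28 visit held on Day 29 or 30, and conflicts with SAP Appendix 1

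*SAP*

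**What the plan says.** - **The window rule.** SAP Appendix 2.1 defines visit windows for reporting but exempts "endpoints assessed for an event through Day 28 (those endpoints use a window of Day 1 to Day 28", as well as PK endpoints.
- **The endpoints.** SAP 3.2.1.2 lists "Proportion of participants with progression of LRTI through Day 3, 5, 15, and 28" and "Proportion of participants with development of LRTI through Day 3, 5, 15, and 28". For both, SAP 6.2.1.2 says: "These endpoints will be summarized with the same methods as the similar endpoint through Day 10". In SAP 3.2.1.1 the Day 10 definitions count an event "at any time up to and including Day 10".
- **How LRTI is observed.** SAP 3.2.1.1: "Presence of LRTI is assessed at each clinic visit". Protocol 8.2.4 has the investigator collect signs and symptoms "during scheduled visits. Criteria for diagnosis of LRTI are provided in Table 3".
- **When the visit may be held.** Protocol Table 1 (Schedule of Activities) allows the Day 28 visit at ±2 days. It schedules an LRTI assessment at Day 28 and none at Day 35, which the schema shows as a phone contact.
- **The label in Appendix 1.** SAP Appendix 1 describes these two endpoints as running through each visit, not through a given day.

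**The concern.** A calendar cut at Day 28 suits hospitalizations, urgent care or ED visits and deaths. These have their own dates, and RSV-related medical visits and admissions are still recorded at Day 35, so an event before the cut can be placed correctly even if it is learned of later.

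LRTI is a status recorded when the participant is seen. If the Day 28 visit takes place on Day 29 or 30, the assessment is compliant with the protocol but lies outside the analysis window, and no later scheduled assessment replaces it. The participant would be reported as free of progression or development through Day 28, although no counted scheduled assessment covers roughly the second half of that period. The two proportions would be somewhat too low, and for these participants the time point in the endpoint's name would not be the one observed.

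**Working it through.** The plan states no figure to reproduce here. The check is a day count, followed by an illustration on stated assumptions.

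**Inputs from the documents**
- Analysis window: Day 1 to Day 28 (SAP Appendix 2.1).
- Day 28 visit: 28 ± 2, that is Days 26 to 30 (Protocol Table 1).
- Day 15 visit: 15 ± 2, that is Days 13 to 17 (Protocol Table 1).

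**Step 1: visit days outside the window.** Allowed days are 26, 27, 28, 29 and 30. Days 29 and 30 lie after the cut: 2 of 5.

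**Step 2: gap in counted follow-up.** If the Day 28 visit is late, the last counted scheduled LRTI assessment is the Day 15 visit. The gap to Day 28 is 28 − 17 = 11 days to 28 − 13 = 15 days.

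**Step 3: is the lost event really a through-Day-28 event?** Often it is. Protocol Table 3 requires the findings to have lasted at least 24 hours, so LRTI that meets the definition on Day 29 would normally have begun by Day 28. LRTI recorded on Day 30 may have begun on either side of the cut.

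**Step 4: does anything else capture it?** In part.
- SAP 6.2.1.1.2.1 and 6.2.1.1.3.1 count RSV-related hospitalization and death as events, whatever the visit date.
- The unplanned post-treatment ARI visit (Day 6 to 28) includes an LRTI assessment. Under Protocol 8.2.5 it is meant for participants who had reached clinical Resolution, and it is not needed when a planned visit falls within 3 days of symptom onset. Symptoms starting on Days 26 to 28 may thus properly wait for a visit on Day 29 or 30.

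What remains uncounted is non-hospitalized, non-fatal LRTI (or progression to severe LRTI) first recorded at a late Day 28 visit.

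**Step 5: size.** Let q be the share of Day 28 visits held on Day 29 or 30, and e the proportion of participants whose first LRTI or progression is found at the Day 28 visit. If lateness is unrelated to the finding, the undercount is q × e. The documents give neither value. I assume q = 10% to 40% (40% is 2/5, visits spread evenly over the five days) and e = 1% to 5%. Undercount in percentage points:

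| q | e = 1% | e = 3% | e = 5% |
|---|---|---|---|
| 10% | 0.1 | 0.3 | 0.5 |
| 20% | 0.2 | 0.6 | 1.0 |
| 40% | 0.4 | 1.2 | 2.0 |

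With the Day 28 visit counted to Day 30, none of the five allowed days falls outside and this undercount is zero.

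**The case against.** The best counter-argument is that the exemption may never have been meant for LRTI. Appendix 2.1 does not name the endpoints it exempts. Appendix 1 keeps the Day 28 wording for hospitalization, medical visits, hospital-free days and hospital or ICU days, and describes the LRTI endpoints by visit. SAP 6.2.1.2 ties the Day 28 versions to the Day 10 endpoint, which is not exempt. On that reading a late visit counts already. This stands as evidence of ambiguity, but it does not settle the matter: SAP 2.2 and 3.2.1.2 name the LRTI endpoints through Day 28, so they meet the literal wording of Appendix 2.1, and no text gives Appendix 1 precedence.

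The window table itself is not in the available text, and endpoint derivations are deferred to an Analysis and Reporting plan that is not available. The table cannot help endpoints taken out of it; the other plan might.

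A reader might infer four stronger things that the documents do not support:
- **That one late record counts for resolution or improvement while being ignored for development.** Resolution and improvement require LRTI at randomization and development requires none, so the populations are disjoint. For progression the overlap is limited to participants with non-severe LRTI at randomization, and it depends on the unseen table. Even there, not resolved and not progressed are compatible results.
- **That 40% of events are lost.** The 40% is an assumed share of visits, not of events.
- **That no LRTI onset date is collected.** SAP 6.6.1 lists items for a baseline summary, not the full CRF.
- **That the key secondary LRTI endpoints are affected.** The sentence in Appendix 2.1 concerns Day 28 only and does not reach the Day 10 endpoints.

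**Conclusion.** The point holds on the SAP as worded, and it is minor. A compliant Day 28 visit on Day 29 or 30 does not count toward LRTI progression or development through Day 28, and Appendix 2.1 and Appendix 1 do not agree on how these endpoints are bounded.

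The day count (2 of 5 allowed days, and 11 to 15 days without a counted scheduled assessment) rests on the documents alone and applies to a participant with no unplanned visit in the gap. The 0.1 to 2.0 percentage points rest on the assumed q and e.

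Only two other secondary proportions at one time point are touched. SAP 2.1 and 5.1 say that the study was discontinued with very few participants and that no inferential testing will be done, so no formal conclusion changes. With so few participants, though, a single misclassified event would show in a reported proportion.

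**What to change.** In SAP Appendix 2.1, limit the Day 1 to Day 28 calendar window to dated events: hospitalization, urgent care or ED visits, and death. Add that LRTI progression and development through Day 28 count the nominal Day 28 visit anywhere within its protocol window, that is to Day 30. This brings Appendix 2.1 into line with Appendix 1.

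The cost is one sentence and a small programming change. The downside is that an LRTI beginning on Day 29 or 30 may occasionally be counted in an endpoint named for Day 28; the same rule would apply in both arms, and a table footnote can disclose it.
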